Study Protocol

Validation Study of a Digital Measurement Device for Central Hand Representation in Children with Neonatal Brachial Plexus Palsy (NBPP)

NCT Number

NCT06950879

Researchers:

[name], [name], [name], [name]. [name]

Date: November 19, 2024

Version: 1.2

1. Introduction

Hand function is one of the most complex sensorimotor skills, requiring both motor output and multisensory input. The brain forms a complex representation of the hand using visual, proprioceptive, and anthropometric information.

This study focuses on **implicit hand representation**, which is influenced by non-visual afferent signals. In children with Neonatal Brachial Plexus Palsy (NBPP), this implicit hand representation appears to be disrupted, leading to altered hand function.

Previous research by [name] et al. showed that the reproducibility of existing test methods is good but that the procedures are cumbersome. This led to the development of the **HANDUZ prototype**, a digitized device that can automatically capture and process hand representation.

This validation study aims to evaluate the **reproducibility** of this prototype in children with NBPP. Reproducibility is measured both **intra-observer** and **inter-observer**.

2. Study Design

Type of study:

Validation study with reproducibility analysis

Design:

This is a single-center, observational reliability study involving children with a confirmed diagnosis of NBPP. Each participant completes six localization trials per hand using the HandUZ device. Two trained raters alternate administration to assess interrater and intrarater reliability. The study is conducted at the Child Rehabilitation Centre of Ghent University Hospital.

Population:

Participants: 18 children aged 8-18 years diagnosed with NBPP.

Inclusion and Exclusion Criteria:

- Inclusion: Children with a confirmed diagnosis of NBPP
- **Exclusion:** Children with other neurological, psychiatric, or physical disorders that could affect hand function

Measurement method:

Participants are seated comfortably in front of a custom-built HandUZ setup, which consists of a three-layered vertical structure: a bottom plate with a measuring mat for hand positioning, a middle plate for visual occlusion, and a top plate holding an overhead webcam. The camera captures an image of the participant's hand for landmark annotation. The tested hand is placed palm-down on the measuring mat, and vision is occluded using the middle plate during the perceptual task.

Each hand is assessed six times in an alternating sequence by two trained raters, following a standardized protocol. The examiner verbally names specific anatomical landmarks—including the centers of the metacarpophalangeal (MCP) joints, fingertips, and wrist styloid processes—and the child uses the index finger of the contralateral (non-tested) hand to localize the

corresponding point on the occluded test hand. The examiner then digitally records the judged location on the computer interface.

The estimated finger length (FL) is calculated using the Euclidean distance between each fingertip and the corresponding MCP joint, as identified during the perceptual task. These values are averaged across two trials to obtain a representative estimated FL for each finger.

Separately, the actual FL is calculated from the image of the participant's hand (taken before the task), using the same anatomical landmarks. For each finger, the percentage overestimation (OE) is calculated using the following formula:

OE (%) = 100 × [(Estimated FL – Actual FL) / Actual FL]

Negative values indicate underestimation while positive values indicate overestimation.

To account for potential learning effects, non-consecutive trials are averaged (e.g., trials 1 and 5; 2 and 6). These averaged values are then used for reliability analyses.

3. Statistical methods

A detailed SAP is included in a separate section and outlines the statistical procedures for assessing reliability, learning effects, and assumption checks. All analyses were conducted using IBM SPSS Statistics (Version 29.0.2.0). A significance level of α = 0.05 was applied. ICC(3,1) was used for reliability analysis, and repeated-measures ANOVA assessed learning effects. Assumption checks included Shapiro-Wilk tests and Mauchly's test for sphericity.

4. Reporting of Results

- Tables: ICC values for intra- and inter-observer reproducibility with 95% confidence intervals
- **Graphs:** Bland-Altman plots to visualize measurement differences and detect systematic bias
- **Conclusions:** Whether the HANDUZ system provides reproducible measurements for clinical use. High reproducibility would support its further clinical implementation.

5. Ethical Considerations

The study protocol was approved by the Ethics Committee of Ghent University Hospital (reference B6702024000525) and conducted in accordance with the Declaration of Helsinki. All participants and/or their legal guardians provided written informed consent.

6. Potential Limitations

- Small sample size (17 children) may limit generalizability
- Accuracy of reference point indication by participants may vary, introducing minor measurement errors

7. Study Timeline

• Participant recruitment: 2 months

• Data collection: 2 months

• Data analysis and reporting: 1 month

• Total study duration: ~5 months

Statistical Analysis Plan (SAP)

Validation Study of a Digital Measurement Device for Central Hand Representation in Children with Neonatal Brachial Plexus Palsy (NBPP)

NCT Number

NCT06950879

Researchers:

[name], [name], [name], [name]. [name]

Date: November 19, 2024

Version: 1.2

1. Objectives of the Analysis

The primary objective of the statistical analysis is to evaluate the reliability of the HandUZ device in measuring implicit finger length (FL) in children diagnosed with Neonatal Brachial Plexus Palsy (NBPP). Specifically, the study aims to assess:

Intrarater reliability – the consistency of repeated measurements taken by the same examiner across different time points.

Interrater reliability – the agreement between two independent raters conducting the same measurement protocol.

A secondary objective is to examine trial-related improvement, defined as progressive changes in estimated FL over successive trials, which could impact the reliability of measurements.

2. Data Preprocessing

Prior to statistical analysis, data preprocessing was performed to ensure data integrity and prepare the dataset for analysis. The following steps were taken:

Visual inspection of each hand map to identify trials that could not be reconstructed due to technical issues or incorrect landmark placement.

Exclusion of trials (7 out of 204, i.e., 3.4%) with unusable data, while retaining the second valid trial if only one of a pair was excluded.

Identification and treatment of missing values in accordance with predefined handling procedures.

Verification of the correct assignment of trials to the respective raters and measurement rounds to preserve the study protocol structure.

3. Descriptive Statistics

Descriptive statistics were computed for:

- Participant demographics (age, sex, lesion characteristics, handedness).
- Actual finger length (in cm) per hand.
- Estimated finger lengths derived from the HandUZ measurements.

- Percentage overestimation (OE) of FL using the formula: OE (%) = 100 × [(Estimated FL Actual FL) / Actual FL].
- Standard deviations, minimum and maximum values, and ranges were calculated to assess interindividual variability.

4. Assumption Checks

Before performing parametric tests, statistical assumptions were evaluated:

- Normality of the estimated FL data at each measurement point was tested using the Shapiro-Wilk test.
- Visual inspection of Q-Q plots was used to confirm approximate normal distribution.
- Sphericity was assessed using Mauchly's test in the repeated-measures ANOVA.
 Where this assumption was violated, Greenhouse-Geisser corrections were applied to adjust the degrees of freedom and maintain valid significance testing.

5. Trial-related improvement Analysis

To assess whether children's performance improved or changed due to increased task familiarity, a learning effect analysis was performed:

A repeated-measures ANOVA was conducted separately for each hand using the four trials administered by Rater 1 (M1, M2, M5, M6). The independent variable was 'time', with four within-subject levels representing the measurement rounds.

When Mauchly's test indicated a violation of sphericity, the Greenhouse-Geisser correction was applied. Polynomial contrast analysis was used to test for linear and higher-order trends.

Visual inspection of estimated marginal means was used to identify systematic trends and interpret borderline findings.

6. Reliability Analyses

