6.1. Intrarater Reliability

Intrarater reliability was assessed using Intraclass Correlation Coefficients (ICCs), based on a two-way mixed-effects model, single measures, with absolute agreement (ICC(3,1)).

Two independent sets of measurements by Rater 1 were averaged:

- Average 1 = Mean of M1 and M5
- Average 2 = Mean of M2 and M6

ICCs were calculated separately for the left and right hands.

Confidence intervals (95%) and F-tests were reported to assess the significance of the

ICCs. Interpretation followed Koo and Li's guidelines:

- ICC < 0.5 = poor
- $-0.5 \le ICC < 0.75 = moderate$
- $-0.75 \le ICC < 0.90 = good$
- ICC ≥ 0.90 = excellent

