6.2. Interrater Reliability

Interrater reliability was evaluated using the same ICC model (ICC(3,1)). Average 3 (M2 and M5 by Rater 1) was compared with Average 4 (M3 and M4 by Rater 2). Separate ICCs were computed for each hand. Confidence intervals and significance levels were reported to quantify rater agreement.

7. Handling of Multiple Testing

This validation study focused on a limited number of predefined analyses, thus adjustments for multiple comparisons were not applied. Nevertheless, the potential for Type I error was minimized by restricting analyses to those aligned with the stated study objectives. Effect sizes (partial η^2) were reported alongside p-values for ANOVA results to aid interpretation and assess the magnitude of learning effects.

8. Software

All statistical analyses were performed using IBM SPSS Statistics (Version 29.0.2.0, IBM Corp., Armonk, NY, USA). Data preprocessing and visualization of hand maps were conducted using custom-built software in Python (Spider 3.0).

9. Significance Thresholds

All statistical tests were two-tailed. The threshold for statistical significance was set at:

- $\alpha = 0.05$
- Confidence intervals were set at 95%.
- For repeated-measures ANOVA, partial eta squared (η^2) was reported as the measure of effect size.

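### ICCs on estimated finger length include true hand size, so they cannot by themselves show that the size-corrected score (OE%) is reproducible; OE% ICCs should be added beside them

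*SAP*

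**What the plan says.** SAP section 1 sets the primary objective, to "evaluate the reliability of the HandUZ device in measuring implicit finger length (FL) in children", and defines trial-related improvement as "progressive changes in estimated FL over successive trials". SAP section 4 adds: "Normality of the estimated FL data at each measurement point was tested using the Shapiro-Wilk test".

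SAP 6.1 states: "Two independent sets of measurements by Rater 1 were averaged" (M1 with M5, and M2 with M6). SAP 6.2 states: "Average 3 (M2 and M5 by Rater 1) was compared with Average 4 (M3 and M4 by Rater 2". Both give the ICC model, the trials and the split by hand. Neither names the quantity averaged, or says whether an ICC is per finger, on a mean over fingers, or on pooled fingers.

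In the SAP, OE% appears only in section 3, among the descriptive statistics: "Percentage overestimation (OE) of FL using the formula". Protocol section 2 defines OE% for each finger, with actual FL taken from an image made before the task. Its closing sentence on averaged values for the reliability analyses follows the OE formula and could mean either score.

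Protocol section 1 presents the prototype as "a digitized device that can automatically capture and process hand representation". Protocol section 4 plans ICC tables and Bland-Altman plots, and a conclusion on whether measurements are reproducible enough for clinical use. The population entry reads: "Participants: 18 children aged 8-18 years diagnosed with NBPP".

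**The concern.** An ICC is the share of total variance that lies between children. Estimated FL contains actual FL as a factor, and children of 8 and of 18 can be expected to differ in hand size. Part of a high FL ICC may then only say that children with longer fingers point to longer distances. That is consistent with FL as an outcome, but it is not evidence that the device reproducibly separates children by how far their hand representation departs from the real hand.

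The Protocol's interest is hand representation, and OE% is the score it defines to take hand size out. If the study reports a good FL ICC and concludes that hand representation is measured reproducibly, that conclusion rests on a quantity that does not isolate it.

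**Working it through.** **Which variable.** The SAP's primary objective, secondary objective and normality check all refer to FL; OE% is only described. The Protocol's averaging sentence leaves OE% possible. FL is the likely ICC variable, and no section explicitly plans an ICC for OE%.

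**Algebra.** Rearranging the documents' formula gives estimated FL = actual FL × (1 + OE/100). Actual FL therefore contributes to the numerator of an FL ICC. Within one child's finger, actual FL is a single fixed value, so OE% is a linear rescaling of estimated FL: repeat-to-repeat error carries over between scales, but the between-child variance does not.

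**No figure to reproduce.** The documents give no target ICC, sample-size calculation, spread of FL or spread of OE. Everything below is assumed and illustrative.

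**Limiting case.** Assume mean actual FL 6.5 cm with coefficient of variation 15%, OE of −25% in every child (no true OE differences), and error SD 0.3 cm for a two-trial average.
- SD of true estimated FL = 6.5 × 0.15 × 0.75 = 0.731 cm; variance 0.535.
- FL ICC = 0.535 / (0.535 + 0.090) = 0.86, while the OE% ICC is 0.
- With error SD 0.2 or 0.5 cm the FL ICC is 0.93 or 0.68; the OE% ICC stays at 0.

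**Grid.** Assume mean actual FL 8 cm with SD s; OE with mean μ and between-child SD b points; correlation r between actual FL and OE; error SD of a two-trial score 8 points; no rater bias. With m = 1 + μ/100, t = b/100 and c = r·s·t:
- ICC(OE) = b² / (b² + 64)
- V = 64t² + m²s² + 16mc + s²t² + c²
- N = 0.0064 × (64 + s²)
- ICC(FL) = V / (V + N)

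Worked cells at b = 12, s = 1.0, where N = 0.0064 × 65 = 0.416 and ICC(OE) = 144/208 = 0.69:
- μ = 0, r = 0: V = 0.9216 + 1 + 0.0144 = 1.936; ICC(FL) = 0.82.
- μ = −20, r = −0.5: V = 0.9216 + 0.64 − 0.768 + 0.0144 + 0.0036 = 0.8116; ICC(FL) = 0.66.

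FL ICCs at b = 12 (OE% ICC 0.69 throughout):

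| Mean OE | r | s = 0.6 | 0.8 | 1.0 | 1.2 cm |
|---|---|---|---|---|---|
| 0 | 0 | 0.76 | 0.79 | 0.82 | 0.85 |
| 0 | −0.3 | 0.70 | 0.73 | 0.77 | 0.80 |
| 0 | −0.5 | 0.63 | 0.66 | 0.70 | 0.747 |
| −20% | 0 | 0.74 | 0.76 | 0.79 | 0.82 |
| −20% | −0.3 | 0.68 | 0.70 | 0.73 | 0.76 |
| −20% | −0.5 | 0.63 | 0.64 | 0.66 | 0.69 |

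All three values of b, 24 cells each, using the SAP's bands (moderate from 0.5, good from 0.75):

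| b | OE% ICC | FL ICC higher | FL good, OE% moderate |
|---|---|---|---|
| 8 | 0.50 | 22 | 4 |
| 12 | 0.69 | 18 | 10 |
| 16 | 0.80 | 13 | 0 (both good in all 24) |

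One of the 18 at b = 12 is higher by only 0.001. The gap reverses when larger hands go with sufficiently lower OE. At b = 12 the break-even r for s = 0.6 / 0.8 / 1.0 / 1.2 is −0.31 / −0.42 / −0.52 / −0.63 at mean OE 0, and −0.25 / −0.33 / −0.42 / −0.50 at mean OE −20%. Making the error constant in cm (0.64 cm) moves no FL ICC at b = 12 by more than 0.005 and leaves the OE% ICC at 0.68 to 0.69.

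**The case against.** The strongest reply is that FL is the stated objective, so an FL ICC is the planned answer to the planned question. That stands, and the FL ICCs should stay. A reader might infer that the FL ICC is the wrong analysis; for the SAP's literal objective it is not. The limit concerns only what may be concluded about hand representation.

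A reader might also infer that the ICC variable is wholly open. Read as a whole, the SAP points to FL. Missing wording in 6.1 and 6.2 would by itself be a matter of detail, although the finger level really is unstated.

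Second, the Protocol's Bland-Altman plots rest on within-child differences, which between-child hand size does not drive as it drives an ICC. This covers part of the problem. But the plots are not carried into the SAP and their scale is not named.

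Third, an OE% ICC has a weakness of its own. Actual FL comes from one image, so its error is common to all repeats and counts as between-child variance. SEM and limits of agreement do not reveal it either. This is a reason to read the OE% results with a stated limitation, not a reason to omit them.

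Finally, the count of 10 of 24 band crossings depends on an OE% ICC of 0.69, not far below the 0.75 cut. Over all three spreads it is 4 + 10 + 0 = 14 of 72. That objection is fair, and the point does not rest on that count.

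**Conclusion.** The point holds in a limited form and is worth fixing because the remedy is cheap. If the ICCs are on estimated FL, as the SAP indicates, they contain hand-size variance and cannot by themselves support a conclusion about the reproducibility of OE%. This follows from the documents' formula and needs only that actual FL varies between children.

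A reader might infer that the FL ICC overstates reliability. The documents do not support that: they give neither the spread of actual FL, nor the spread of OE, nor their correlation, and under the assumed inputs the gap can be large, negligible or reversed. Size and direction are unknown; confidence is medium. If the ICCs were already computed on OE%, the hand-size issue falls away and only the wording remains.

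**What to change.** - In SAP 6.1 and 6.2, name the variable and the finger level, and keep the FL ICCs for the stated objective.
- Beside them, report intrarater and interrater ICCs with 95% CI on OE%, using the same trial averages, per hand and at the stated finger level.
- Carry the Protocol's Bland-Altman analysis into the SAP, with SEM and limits of agreement in OE points.
- Base any conclusion about reproducible hand representation on the OE% ICCs and limits of agreement together, not on the FL ICC alone.
- State as a limitation that error in the single pre-task image is shared across repeats, counts as between-child variance in the OE% ICC, and is not shown by SEM or limits of agreement.
- The SAP already reports trial exclusions, so if the OE% ICCs were not in the original analysis, label them as added later.

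The cost is SAP wording and at most a small rerun on a score that is already calculated. The OE% ICCs may turn out lower than the FL ICCs.

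### Does the missing-trial rule leave the four-level learning ANOVA in SAP section 5 without enough children, so that the analysis should change?

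*SAP*

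**What the plan says.** SAP section 1 makes learning a secondary objective, defined as "progressive changes in estimated FL over successive trials". Section 5 tests it: "A repeated-measures ANOVA was conducted separately for each hand using the four trials administered by Rater 1 (M1, M2, M5, M6"). Time is the factor, "with four within-subject levels representing the measurement rounds", and "Polynomial contrast analysis was used to test for linear and higher-order trends". Estimated marginal means are also inspected by eye.

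Section 2 describes the missing data. Hand maps were inspected for "trials that could not be reconstructed due to technical issues or incorrect landmark placement". The result was "Exclusion of trials (7 out of 204, i.e., 3.4%) with unusable data", with the explicit rule of "retaining the second valid trial if only one of a pair was excluded". A further step reads "Identification and treatment of missing values in accordance with predefined handling procedures". Neither document sets out what those procedures are.

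Sections 6.1 and 6.2 build the ICCs from two-trial averages: M1 with M5, M2 with M6, M2 with M5 (all Rater 1), and M3 with M4 (Rater 2).

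**The concern.** The explicit rule is written for pairs, and section 5 has none. If M1 is unusable, M5 can stand in for the M1 and M5 average, but the M1 level of the ANOVA stays empty. A repeated-measures ANOVA run in the usual way then drops the child from that hand's test, three valid trials included. A loss of 3.4% of trials could become a much larger loss of children in a study of about 17. Neither document plans to report the number analysed per hand, so a reader might not notice that the learning test and the ICCs rest on different children. The SAP says learning could affect reliability, and a non-significant learning test on fewer children could be read as more reassuring than it is. A mixed model using every valid Rater 1 trial looks like an easy remedy.

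**Working it through.** **Inputs.** Six trials per hand (Protocol section 2); 17 children (Protocol section 6); 7 of 204 trials excluded (SAP section 2); four Rater 1 trials and two Rater 2 trials per child-hand set (SAP sections 5 and 6.2). Where the 7 exclusions fell is not stated, so a range is needed.

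**The plan's own figure.** 17 × 2 × 6 = 204 and 7/204 = 3.4%, as stated. The 18 children in Protocol section 2 would give 18 × 2 × 6 = 216, so 17 is used here. There are 17 × 2 = 34 child-hand sets.

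**Loss if the ANOVA is complete-case.**
- Bounds: 0 sets if all 7 exclusions are M3 or M4; 7 sets if all are Rater 1 trials in different sets.
- Scattered at random: chance that a set loses a Rater 1 trial = 1 − C(200,7)/C(204,7) = 0.131. Expected loss = 34 × 0.1313 = 4.46 sets, or 17 × 0.1313 = 2.23 children per hand. Chance that a given hand loses at least one child = 1 − C(136,7)/C(204,7) = 0.944.
- Clustered in k sets: expected loss per hand = k × [1 − C(6k−4,7)/C(6k,7)]/2. For k = 2: 2 × (1 − 8/792)/2 = 0.99. For k = 3: 3 × (1 − 3432/31824)/2 = 1.34.

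**Does an affected child stay in the ICCs?** A child leaves an ICC when both trials of one average are gone. With 7 exclusions placed at random within two sets, a given set is affected in the ANOVA in 792 − 8 = 784 of 792 placements. Both members of some pair are missing in 624 of these (3×6 + 14×15 + 15×20 + 6×15 + 1×6), so 624/784 = 80% also leave an ICC. For three sets the same count gives 13014/28392 = 46%. Under random scatter over all 204 trials it is about 2%.

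**Power of the linear trend.** The documents give no effect size, so this is illustrative: a one-sample t test on contrast scores with standardised effect 0.724, chosen to give 80% at n = 17, one row per child.

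| Children affected | Complete-case | Mixed model, all valid trials | Gain (points) |
|---|---|---|---|
| 1 (n = 16) | 77.2% | 78% to 79% | 1 to 2 |
| 2 (n = 15) | 74.1% | 78% | about 4 |
| 3 (n = 14) | 70.7% | 76% to 78% | 5 to 7 |

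The mixed-model figures come from simulation: unstructured covariance, child SD 2, residual SD 1, child-slope SD 0 to 0.3 per trial, exactly one Rater 1 trial missing per affected child, degrees of freedom set to complete cases minus 1.

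**What the mixed model costs.** With two children affected, its omnibus test has 53% to 56% power against 59% to 73% for the ANOVA F. A simpler fallback with random intercept and slope reaches 74% to 77% for the trend, against 74.1% complete-case. A random intercept alone inflates type I error to 9% to 12% when children differ in slope.

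**Can a reader recover n?** The ANOVA has 3 and 3(n − 1) degrees of freedom: 48 error degrees of freedom at n = 17 and 42 at n = 15. Greenhouse-Geisser multiplies both by the same factor, so their ratio remains n − 1. An F statistic printed with its degrees of freedom shows how many children were used, provided rows are children.

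**The case for a change.** The strongest case for acting is that the gap is real. The pair rule cannot serve section 5, the other procedures are named without content, and under random scatter a given hand would almost certainly (94%) lose a child. Stating the rule and n per hand costs a few sentences. The mixed model keeps data already collected, and its simulated type I error was acceptable (4.5% to 5.1%).

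The arithmetic stands, and so does the wish to see n per hand and the excluded trials listed. The rest carries less weight:

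- A procedure whose content is not printed is not the same as no procedure. The documents do not show that the ANOVA was complete-case.
- The contrast between a child dropped from the ANOVA and kept in the ICCs holds only if the exclusions are scattered. The causes section 2 names could well cluster within a child or session, and then many affected sets leave an ICC as well.
- The power gain assumes one missing trial per affected child. In the clustered case most affected sets miss two or more, leaving a model less to recover. The simulated degrees of freedom are also only one of several small-sample choices.
- Neither analysis protects against bias if landmark errors track the child's own result.

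**Conclusion.** This is missing detail on a secondary objective, of a kind analysts normally settle in the write-up; the planned analysis can stand. If the ANOVA is complete-case, the loss is 0 to 7 of 34 child-hand sets, with 2.2 of 17 children per hand expected under random scatter and 1.0 to 1.3 under clustering in two or three sets. In the illustrative setting, losing two children takes trend power from 80% to 74%. No ICC calculation depends on the ANOVA.

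Replacing or supplementing the ANOVA is a trade-off without a clear gain. It offers 1 to 7 points on one contrast under assumed inputs, against an unstructured covariance estimated from 17 children, a weaker omnibus test that would keep the ANOVA alongside it, and a fallback that gains little. The SAP already reports the exclusions as made, so the model would be chosen after they were known. As an optional sensitivity analysis labelled post hoc it would do no harm.

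The conclusion rests on 17 children (from the 204 trials), one row per child, and missing-value procedures that exist as section 2 says. The natural place for the numbers analysed and the identity of the 7 trials is the results report.

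### The SAP does not give the spacing of the polynomial trend contrasts, although two Rater 2 trials fall between the second and third 'time' levels; equal spacing would turn a small part of steady learning into a cubic term

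*SAP*

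**What the plan says.** SAP section 1 defines the secondary objective, trial-related improvement, as "progressive changes in estimated FL over successive trials". Protocol section 2 describes the schedule: "Each hand is assessed six times in an alternating sequence by two trained raters, following a standardized protocol".

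SAP section 5 takes only Rater 1's four trials (M1, M2, M5, M6), separately for each hand, in a repeated-measures ANOVA: "The independent variable was 'time', with four within-subject levels representing the measurement rounds". It continues: "Polynomial contrast analysis was used to test for linear and higher-order trends". Estimated marginal means are also inspected by eye to identify trends and to interpret borderline results.

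SAP section 6.2 shows who ran the other two trials: "M3 and M4 by Rater 2". The M number is the trial order: the protocol's example of averaging trials 1 with 5 and 2 with 6 matches the pairs M1/M5 and M2/M6 in SAP section 6.1.

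Neither document gives a numeric spacing for the contrasts or mentions the gap between M2 and M5.

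**The concern.** A polynomial contrast is defined only once the positions of its levels are fixed. Here the child performs the same localization task twice more between the second and third level, so the steps by trial number are 1, 3, 1. Four levels described without qualification suggest steps of 1, 1, 1. Contrasts built on equal steps would read part of a straight line as a higher-order trend. Marginal means plotted at equal steps would show an apparent jump between the second and third round.

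What is at stake is the description of learning in the secondary analysis. The SAP tests higher-order trends explicitly and makes no multiplicity adjustment (section 7), so an inflated cubic test has no other safeguard.

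**Working it through.** The documents give no power or trend figure for this analysis, so there is none to reproduce.

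**Inputs**
- Level positions by trial number: 1, 2, 5, 6 (SAP sections 5 and 6.2; protocol section 2).
- Children: 17. The protocol's limitations section says 17, and the SAP's 204 trials equal 17 × 2 hands × 6. The protocol's population entry says 18.
- Two-sided α = 0.05 (SAP section 9).
- Assumed: slopes of 0.1 to 0.5 trial SD per trial, where trial SD means the within-child residual SD and is also the error SD of each normalised contrast. The documents give neither an SD nor a learning effect.
- Assumed: a trial under Rater 2 gives as much practice as one under Rater 1.

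**Step 1: split a straight line with equal-spacing weights.** Let y = (1, 2, 5, 6), mean 3.5. Total SS = 2.5² + 1.5² + 1.5² + 2.5² = 17.0. Each contrast's SS is (c′y)² / (c′c).

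| Contrast | Weights | c′y | c′c | SS | Share |
|---|---|---|---|---|---|
| Linear | −3, −1, 1, 3 | 18 | 20 | 16.2 | 95.3% |
| Quadratic | 1, −1, −1, 1 | 0 | 4 | 0 | 0% |
| Cubic | −1, 3, −3, 1 | −4 | 20 | 0.8 | 4.7% |

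With the real positions, the linear weights are −2.5, −1.5, 1.5, 2.5 and steady learning is 100% linear.

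**Step 2: effect on the tests.** Each contrast is tested by F(1, 16) with noncentrality 17 × SS × s², where s is the slope in trial SD per trial. For the cubic term at s = 0.2 this is 17 × 0.8 × 0.04 = 0.544.

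| Slope s | Cubic significant, equal spacing | Linear power, equal spacing | Linear power, real spacing |
|---|---|---|---|
| 0.1 | 6.4% | 34.5% | 35.9% |
| 0.15 | 8.2% | 64.7% | 66.8% |
| 0.2 | 10.7% | 87.6% | 89.1% |
| 0.3 | 18.0% | 99.7% | 99.8% |
| 0.5 | 41.0% | about 100% | about 100% |

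With the real spacing, the cubic test keeps its 5% under steady learning. The largest loss of linear power in the table is 2.1 points, at s = 0.15.

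**Step 3: what does not change.** The omnibus F uses the total of 17.0 however it is divided. The omnibus p-value, its partial eta squared and the Mauchly and Greenhouse-Geisser steps are therefore the same under either spacing.

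**Step 4: does the trend's shape bear on the ICCs?** Compare the mean trial positions of the averages in SAP sections 6.1 and 6.2.
- Intrarater: (1 + 5)/2 = 3 against (2 + 6)/2 = 4. Linear learning leaves a one-trial step. A quadratic centred at 3.5 cancels: (6.25 + 2.25)/2 = 4.25 on both sides.
- Interrater: (2 + 5)/2 = 3.5 against (3 + 4)/2 = 3.5. Linear learning cancels. A cubic centred at 3.5 also cancels, since each pair is symmetric about 3.5. A quadratic does not: 2.25 against 0.25.

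**The case against.** The strongest reply is that the SAP never says equal spacing was used. The analyst may have entered 1, 2, 5, 6, in which case nothing was misread. That stands: the documents show an unstated metric, and the misreading is conditional on equal spacing.

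Second, the effect is small. Most of the trend stays linear, and the reported omnibus result and effect size are untouched. The 41% figure needs 0.5 SD per trial, or 5 × 0.5 = 2.5 SD between the first and sixth trial, where learning would be unmistakable anyway. This also stands and sets the severity.

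Third, 1, 2, 5, 6 is itself an assumption. If only Rater 1's trials produced learning, equal spacing would be right and the real-number metric would create the same 4.7% cubic share. That is a reason to state the assumption. It is not a reason to leave the spacing open, because the task is the same under both raters and the objective concerns successive trials.

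A reader might infer that a false cubic undermines the ICCs, on the view that straight-line learning is harmless to them and curvature is not. Step 4 does not support this. Linear learning leaves a step in the intrarater comparison, and a centred cubic cancels in the interrater one. The SAP also has no rule linking trend shape to the averages.

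A reader might also conclude that leaving out M3 and M4 is an error and that a six-trial contrast should lead. Six trials give a linear SS of 2 × (6.25 + 2.25 + 0.25) = 17.5, only 2.9% above the correctly spaced 17.0. Excluded trials can cancel that gain. If the 7 exclusions in 204 fall at random and only complete series are used, about (197/204)⁶ = 81% of series keep six trials and (197/204)⁴ = 87% keep four, so 17.5 × 0.81 = 14.2 against 17.0 × 0.87 = 14.8. Restricting the test to Rater 1 is a defensible way to keep rater differences out.

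**Conclusion.** The point holds as a minor gap in specification. SAP section 5 tests linear and higher-order trends on levels that lie at trials 1, 2, 5 and 6 without giving the spacing. If the levels were taken as equally spaced, 4.7% of steady learning goes into the cubic term. The cubic test then exceeds its nominal 5%, from slightly (about 6% at 0.1 trial SD per trial) to substantially (41% at 0.5).

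The rates rest on 17 children, constant learning per trial, equal practice under both raters, and slopes that the documents do not supply. A significant cubic term, or a jump in the plotted means, should not be read as curvature until the spacing is known. The documents do not show that a misreading occurred, and nothing here bears on the validity of the ICCs.

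**What to change.** In SAP section 5:
- State the polynomial metric and set it to the real trial numbers 1, 2, 5, 6.
- Plot the estimated marginal means against real trial number, with the gap for M3 and M4 visible.
- State the assumption that Rater 2 trials give the same practice as Rater 1 trials.

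A trend over all six trials with a rater term may be added as a supportive analysis. The Rater 1 analysis should stay as the main result.

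The cost is one line of SPSS syntax, a relabelled plot axis and a sentence of text, with no new data. If the metric was already 1, 2, 5, 6, stating it closes the point apart from the plot axis and the practice assumption.
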